Grade 1 anorexia	Maintain dose. Rule out other causes. Consider nutritional consultation and use nutritional supplements (eg, Ensure [®] , Boost [®]). For persistent symptoms, start appetite stimulants, such as olanzapine (2.5 to 5 mg PO every morning) or megestrol acetate (400 mg QD), per NCCN guidelines.
Grade 1 weight loss Grade 2 anorexia	Initiate appetite stimulants, such as olanzapine (2.5 to 5 mg PO every morning) or megestrol acetate (400 mg QD), as per NCCN guidelines.
Grade 2 weight loss Grade 3 anorexia, or Grade 3 weight loss	Interrupt selinexor dosing until improved to Grade 1 or baseline and weight stabilizes. Reduce selinexor by 1 dose level. Rule out other causes. Consider nutritional consultation and use nutritional supplements (eg, Ensure [®] , Boost [®]) Start appetite stimulants as above,

Toxicity and Intensity	Supportive Care and Dose Adjustment Guidelines
Nausea, Acute	
Grade 1 or 2	
Maintain dose. Rule out other causes. Use standard additional anti-nausea medications to supplement the protocol-required 5-HT3 antagonists.
 
Use additional anti-nausea medications to supplement the protocol-required 5-HT3 antagonist(s). Olanzapine 2.5 to 5 mg PO every morning, per NCCN guidelines, can mitigate nausea and anorexia.

Grade 3	
Rule out other causes. Use additional anti-nausea medications to supplement the protocol-required 5-HT3 antagonist(s). Olanzapine 2.5 to 5 mg PO every morning, per NCCN guidelines, can mitigate nausea and anorexia.
 
Interrupt selinexor dosing until resolved to Grade ≤ 2 or baseline and reduce selinexor by 1 dose level.
 
Patients with significant nausea/vomiting after several doses of selinexor may have an antitumor response. Consider an unscheduled assessment of tumor response as part of the patient's evaluation.

Hyponatremia	
Grade 1 (sodium levels < Normal to 130 mmol/L)	
Maintain dose. Rule out other causes including drug (eg, diuretic) effects. Be certain that reported sodium level is corrected for concurrent hyperglycemia (serum glucose >150 mg/dL).
 
Treat hyponatremia per institutional guidelines including dietary review. Provide supplemental oral and/or intravenous fluids if dehydration is present. Consider addition of salt tablets to patient's diet.

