Grade 3 with sodium levels <130-120 mmol/L without symptoms	
Rule out other causes including drug (eg, diuretic) effects. Be certain that reported sodium level is corrected for concurrent hyperglycemia (serum glucose >150 mg/dL).
 
If (corrected) sodium is Grade ≤ 3 and continues to be asymptomatic, then patient may continue current dosing without interruption provided that IV saline and/or salt tablets are provided and patient is followed closely.
 
If Grade 3 is persistent or worsens or does not respond to treatment, interrupt selinexor dosing until resolved to Grade 1 or baseline and reduce selinexor by 1 dose level.

Grade 3 with sodium levels <130-120 mmol/L with symptoms or Grade 4 (<120 mmol/L)	
Rule out other causes including drug (eg, diuretic) effects. Be certain that reported sodium level is corrected for concurrent hyperglycemia (serum glucose > 150 mg/dL).
 
Interrupt selinexor dosing until resolved to Grade 1 or baseline and without symptoms. Reduce selinexor by 1 dose level.

Diarrhea	
Grade 1	
Maintain dose. Rule out other causes including drug effects. Treat per institutional guidelines with anti-diarrheals, such as loperamide.

Grade 2	
Rule out other causes including drug effects. Treat per institutional guidelines with anti-diarrheals. Interrupt selinexor dosing until resolved to Grade 1 or baseline.
 
For first occurrence, restart selinexor at current dose.
 
For \geq second occurrence, reduce selinexor by 1 dose level.

Grade 3 or 4	
Interrupt selinexor dosing until resolved to Grade 1 or baseline and patient is clinically stable. Reduce selinexor dose by 1 dose level.

Thrombocytopenia	
Grade 1 or 2	
Maintain dose. Rule out other causes including drug effects.

Toxicity and Intensity	Supportive Care and Dose Adjustment Guidelines

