Grade 2 or 3	Hold until therapeutically anticoagulated and platelets are \geq 50,000/mm ³ . Resume at the same dose level.	Hold until therapeutically anticoagulated and platelets are \geq 50,000/mm ³ . Resume at the same dose level.
Recommendation: Anticoagulation (warfarin prohibited)		

Event Name	Hyponatremia	
Grade of Event	Management/Next Dose Ibrutinib	Management/Next Dose of Selinexor
Grade 1 (Lower Limit of Normal to 130 nM)	No change in dose	Maintain selinexor dose and frequency level, assure adequate fluid, electrolyte and caloric intake, adjust other medications, and consider salt supplementation 1-3 times per day. Correct sodium level for hyperglycemia (serum glucose >150 mg/dL). Rule out other causes of low sodium (e.g., SIADH, cardiac, hepatic, adrenal, renal, and thyroid diseases, Fanconi Syndrome, diuretic use, etc.).
Grade 3 (126-129 mmol/L)	No change in dose	Ensure patient is euvolemic and has sufficient fluid and electrolyte intake. Replace fluids orally or IV if patient is dehydrated. Correct sodium level for hyperglycemia. Rule out other causes of low sodium (see above for Grade 1). Hold selinexor until hyponatremia

		resolves to Grade ≤ 1 (≥ 130 nM) and initiate aggressive salt supplementation 2-3 times per day. Restart at the same dose and frequency of selinexor and monitor serum sodium closely. If this recurs, measure urine sodium and creatinine levels to investigate for other causes of hyponatremia.
Grade 3 (120-125 mmol/L)	No change in dose	Hold selinexor dose until sodium ≥ 125 mmol/L*. Decrease selinexor to the next lowest dose level for initial and each subsequent occurrence.

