
*If sodium does not recover to ≥ 125 mmol/L within 14 days of holding selinexor, selinexor should be permanently discontinued
 
 In marked hyperglycemia, ECF osmolality rises and exceeds that of ICF, since glucose penetrates cell membranes slowly in the absence of insulin, resulting in movement of water out of cells into the ECF. Serum Na concentration falls in proportion to the dilution of the ECF, declining 1.6 mEq/ L for every 100 mg/dL (5.55 mmol/L) increment in the plasma glucose level above normal. This condition has been called translational hyponatremia because no net change in total body water (TBW) has occurred. No specific therapy is indicated, because Na concentration will return to normal once the plasma glucose concentration is lowered. Corrected Sodium = Measured sodium + 0.024 * (Serum glucose - 100). 		

Event Name	Anorexia	
Grade of Event	Management/Next Dose Selinexor	
Grade 1		Assess dietary options (e.g., try a variety of other foods). Add high-calorie supplements (e.g., Ensure®). Consider an appetite stimulant(s) (see the NCCN Clinical Practice Guideline for anorexia).
Grade 2		Add high-calorie supplements (e.g., Ensure®). Add an appetite stimulant(s) (see the NCCN Clinical Practice Guideline for anorexia). Selinexor dosing may be interrupted intermittently while supportive medications are instituted, usually for <1 week. If Grade 2 anorexia does not resolve after institution of supportive medications, reduce selinexor dose by 1 level . If patient's anorexia is Grade

		≤1 for 4 weeks, then the dose of selinexor may be increased back to the previous dose level.
Grade 3		Interrupt dosing with selinexor until resolution to Grade ≤2. Add high calorie supplements. As described above, initiate supportive medications for anorexia. Restart selinexor at 1 dose level reduction . once anorexia resolves to Grade ≤ 2 and follow the guidelines above. If patient's anorexia is Grade ≤1 for 4 weeks, then the dose of selinexor may be increased back to the previous dose level.

Event Name	Weight Loss	
Grade of Event		Management/Next Dose of Selinexor
Grade 1		Assess dietary options (e.g. try a variety of other foods). Add high-calorie supplements (e.g., Ensure®). If fatigue or nausea also present, consider corticosteroids on day of and day after selinexor dosing. Consider an appetite stimulant(s) (see the NCCN Clinical Practice Guideline for anorexia and anti-emesis).

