6.5 Conditions not Requiring Dose Reduction

The following conditions are exceptions to the above guidelines. selinexor does not need to be held in the following cases:

- Alopecia of any grade
- Electrolytes abnormalities that are reversible with standard interventions

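### The Section 6.2 hyponatremia footnote gives two different glucose-correction rates for sodium, 1.6 and 2.4 per 100 mg/dL, and they can disagree at the 130 mmol/L dosing cut-off

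*Combined protocol and SAP*

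**What the plan says.** The hyponatremia table in Section 6.2 sets selinexor dosing by sodium band. Grade 1 runs down to 130, and the dose is maintained. In the 126-129 mmol/L band selinexor is withheld until sodium is back at 130 or above, then resumed at an unchanged dose and frequency.

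Sodium must be corrected for high glucose before these bands are applied. The Grade 1 row says "Correct sodium level for hyperglycemia (serum glucose >150 mg/dL", and the 126-129 row repeats the instruction before the hold: "Correct sodium level for hyperglycemia. Rule out other causes of low sodium (see above for Grade 1). Hold selinexor until hyponatremia".

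The footnote to that table explains the correction. Its text describes sodium as "declining 1.6 mEq/ L for every 100 mg/dL (5.55 mmol/L) increment in the plasma glucose level above normal". It ends with the only explicit calculation in the document: "Corrected Sodium = Measured sodium + 0.024 * (Serum glucose - 100" (closing bracket follows).

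The supportive-care table in Section 5.18 also asks for the correction ("Be certain that reported sodium level is corrected for concurrent hyperglycemia (serum glucose >150 mg/dL") but gives no rate and does not point to the footnote. It places the Grade 3 boundary at below 130: "Grade 3 with sodium levels <130-120 mmol/L without symptoms".

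**The concern.** One footnote gives two rates for the same quantity. The text rate is 0.016 per mg/dL and the formula rate is 0.024 per mg/dL. Above the formula's reference glucose, and with the same reference used for the text rate, the formula always returns the higher corrected sodium. The corrected value is compared with 130, which separates maintaining selinexor from holding it, so the choice of rate can change the instruction for a patient near that boundary.

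High glucose is foreseeable here. Both tables set a trigger at 150 mg/dL, Section 5.10 allows medication for diabetes, and Section 5.17 gives dexamethasone 12 mg with each selinexor dose.

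**Working it through.** **Inputs**
- Text rate: 1.6 mEq/L per 100 mg/dL, so 0.016 per mg/dL (Section 6.2 footnote).
- Formula rate: 0.024 per mg/dL, reference glucose 100 (same footnote).
- Correction trigger: glucose above 150 mg/dL (Sections 5.18 and 6.2).
- Dosing cut-off: 130 mmol/L (Section 6.2 bands and release criterion; Section 5.18 Grade 3 row).
- Assumption: normal glucose for the text rate is 100 mg/dL. The text says only that the rise is measured from normal; 100 is the formula's reference value.
- Assumption: the glucose values below are illustrative, because the documents give no glucose data.

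**Step 1: can the formula reproduce the stated rate?** 0.024 × 100 = 2.4 per 100 mg/dL, against 1.6 in the text. It does not. The ratio is 2.4 / 1.6 = 1.5.

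**Step 2: could units explain it?** A glucose of 300 mg/dL is 3 × 5.55 = 16.65 mmol/L. Then 0.024 × (16.65 − 100) = −2.0, a negative correction for a high glucose. The formula therefore has to be read in mg/dL, and the discrepancy stays.

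**Step 3: size of the gap at glucose G.** (0.024 − 0.016) × (G − 100) = 0.008 × (G − 100). This is 0.8 mmol/L at 200, 1.6 at 300 and 2.4 at 400 mg/dL.

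**Step 4: effect at the cut-off, measured sodium 126.**

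| Glucose (mg/dL) | Formula: 126 + 0.024 × (G − 100) | Text rate: 126 + 0.016 × (G − 100) | Side of 130 |
|---|---|---|---|
| 200 | 128.4 | 127.6 | both below |
| 300 | 130.8 | 129.2 | split |
| 400 | 133.2 | 130.8 | both above |

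At 300 mg/dL the formula leads to maintaining selinexor and the text rate to holding it. At 200 and 400 the two agree, so the conflict appears only in part of the glucose range.

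**Step 5: reading 129.2.** No Section 6.2 row prints values between 129 and 130. I treat 129.2 as a hold because it is below the release criterion of 130 and rounds to 129. The documents give no rounding rule.

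**Step 6: sensitivity to the assumed normal glucose.** At glucose 300, the text rate reaches 130 only if normal is 300 − 4/0.016 = 50 mg/dL or lower. If corrected values are rounded to whole numbers, it reaches 129.5 when normal is 300 − 3.5/0.016 = 81.25 mg/dL or lower, and the split disappears. If normal is taken as the 150 mg/dL trigger, the text rate gives 126 + 0.016 × 150 = 128.4 and the split widens.

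**The case against.** The strongest reply is that only one of the two figures is an instruction. The 1.6 sits in a sentence of physiology, while the formula is the one calculation a site is told to perform. If every site uses it, no two sites disagree. This stands. What remains is that every correction is then 1.5 times the rate the footnote states, always in the direction of fewer holds, and a reader cannot tell which figure is the slip.

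The practical effect is also limited, and this stands in full. The 126-129 hold is temporary and carries no dose reduction. The footnote itself says low sodium caused by high glucose needs no specific treatment. For asymptomatic patients at Grade 3 or below, Section 5.18 says "then patient may continue current dosing without interruption provided that IV saline and/or salt tablets are provided". Section 6.5 lists "Electrolytes abnormalities that are reversible with standard interventions" among conditions for which selinexor need not be held. Section 6.7 requires the principal investigator to be consulted on delays and modifications.

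A reader might infer more than the documents support:
- **That sites are applying different rates.** Nothing shows this. It would need a site to set the printed formula aside, for instance when working from Section 5.18.
- **That dose reductions or permanent discontinuation are affected.** The 120-125 row carries those consequences and has a release threshold of 125. Sodium 121 at glucose 300 would give 125.8 by the formula and 124.2 by the text rate. That row does not itself call for the correction, so I do not rely on it.
- **That DLT or the MTD is affected.** The Section 5.3 definition exempts Grade 3 electrolyte abnormalities that supportive therapy can correct, and it does not refer to this footnote.

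**Conclusion.** The footnote is wrong as written: it states 1.6 and 2.4 per 100 mg/dL for the same correction, and no unit or other section reconciles them. The contradiction itself rests on no assumption. That it can change a dosing instruction is shown by the example of sodium 126 at glucose 300 mg/dL (130.8 against 129.2). The example assumes that glucose value, a normal glucose of 100 mg/dL, and that the corrected value decides the band.

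Priority is low. The disputed outcome is a temporary hold that other sections already soften. How often it would arise cannot be shown, because glucose is not in the chemistry list in the Section 10 calendar. No effect on DLT or sample size is shown. It would go too far to say that the formula is the erroneous figure, since the documents do not show which rate was intended.

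**What to change.** State one rate in both places. Changing 0.024 to 0.016 in the formula matches the footnote's text and is the more cautious choice for selinexor dosing. Its small downside is slightly more temporary holds in hyperglycemic patients. If the sponsor confirms that 2.4 was intended, change the sentence to 2.4 and leave the formula alone. A short pointer from the Section 5.18 hyponatremia rows to the formula would be useful but is optional.

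The cost is one line in the footnote, plus the pointer if wanted. Data collection, sample size and analysis are unchanged.

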6.3 Dose Reduction for Decreased Glomerular Filtration Rate (GFR)

Selinexor is not significantly eliminated by the kidney; therefore, no dose alteration of selinexor is required with renal dysfunction. If dialysis is implemented during selinexor treatment, then selinexor should always be given after dialysis. Selinexor tablets are to be taken with at least 120 mL (4 ounces) of fluids (water, juice, etc.) at approximately the same time each day.

6.4 Dose Adjustment for Infection

Patients with active uncontrolled serious or suspected serious infections (i.e. Grade 3 or higher, or Grade 2 or higher at the discretion of the treating physician) should have selinexor and ibrutinib treatment withheld until infection has clinically resolved or stabilized. Dexamethasone should be adjusted per institutional guidelines, and adrenal suppression considered. After the infection has resolved clinically, or the patient's clinical condition has stabilized, treatment with selinexor may continue at the original dose. Missed doses will not be replaced. Patients may continue on antibiotics or other anti-microbial agents for prolonged periods while re-initiating

their selinexor regimen at the discretion of the investigator. Note: selinexor has not been associated with opportunistic infections in approximately 400 patients treated as of 1 August 2014.

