6. DOSING DELAYS/DOSE MODIFICATIONS

Toxicities that occur in cycle 1 that are DLTs (Section 4.2) will result in protocol removal. Adverse events that are not defined as DLTs and / or occur in cycles 2 and higher will lead to dose delays and modifications as detailed below. No dose reduction below ibrutinib 140 mg and selinexor 20 mg/week will be allowed. If a patient experiences several adverse events, and there are conflicting recommendations, the investigator should use the recommended dose adjustment that reduces the dose to the lowest level. Missed doses will not be replaced. Treatment delays for adverse events exceeding 28 days will lead to protocol removal unless approved by the principal investigator.

Ibrutinib-related lymphocytosis, for the purposes of this protocol, is defined as an elevation in blood lymphocyte count of $\geq 50\%$ compared with baseline count in conjunction with unequivocal improvement in at least 1 other disease-related parameter including lymph node size, spleen size,

hematologic parameters (hemoglobin or platelets), or disease-related symptoms. Ibrutinib-associated treatment-related lymphocytosis generally occurs within the first few weeks of therapy, peaks within the first few months, and resolves slowly. Patients with isolated lymphocytosis in the setting of reduced disease burden or improvement in hemoglobin/platelets should not be considered to have progressive disease.

Asymptomatic treatment-related lymphocytosis should not be considered an adverse event. Subjects with treatment-related lymphocytosis in the absence of other disease-related symptoms should be encouraged to remain on study treatment and continue with all study-related procedures.

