6.2 Dose adjustment guidelines for non-hematologic ibrutinib or selinexor-related toxicities

Specific guidelines are provided below for non-hematologic toxicities. For all other grade 3 non-hematologic toxicities possibly related to study therapy, hold the causative agent, or if the causative agent cannot be determined, hold both ibrutinib and selinexor. Once the toxicity is improved to ≤ Grade 2 or until baseline pre-treatment value, resume treatment with a decrease in the dose of ibrutinib by 140 mg or selinexor by one dose level. No dose reduction below ibrutinib 140 mg and selinexor 20 mg/week will be allowed. If a patient experiences several adverse events, and there are conflicting recommendations, the investigator should use the

recommended dose adjustment that reduces the dose to the lowest level. Missed doses will not be replaced. Treatment delays for adverse events exceeding 28 days will lead to protocol removal.

Any Grade 4 toxicities (lasting ≥ 7 days for transaminase or electrolyte abnormalities) that are at least possibly attributed to selinexor or ibrutinib should result in permanent discontinuation of the causative agent. If attribution to a single drug cannot be made, both drugs should be discontinued.

Event Name	Nausea	
Grade of Event	Management/Next Dose Ibrutinib	Management/Next Dose of Selinexor
Grade 1	No change in dose	5-HT3-antagonists, D2-antagonists or NK1 antagonists, or dronabinol or combinations can prevent nausea in the majority of patients. Consider additional anti-emetics (see the NCCN Clinical Practice Guideline for antiemesis). Provide guidance on diet as described above for anorexia as increased caloric intake may reduce nausea.
Grade 2	No change in dose	Implement one or more combinations of anti-nausea medications. Consider additional anti-emetics (see the NCCN Clinical Practice Guideline for antiemesis). If Grade 2 nausea persists, reduce dose of selinexor by one dose level. If patient's nausea is Grade ≤ 1 for 4 weeks, then the dose of selinexor may be increased back to the previous dose level.

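### For a possibly drug-related Grade 4 infection not handled as a Cycle 1 DLT, Sections 6.4, 6.2 and 5.18 give incompatible selinexor rules; Grade 3 has a weaker form of the conflict

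*Combined protocol and SAP*

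**What the plan says.** Four parts of the protocol bear on dosing after a serious infection.

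- **Section 6.4 (infection).** It applies to active, uncontrolled infections that are serious or suspected to be so, defined as "i.e. Grade 3 or higher, or Grade 2 or higher at the discretion of the treating physician". Selinexor and ibrutinib are both withheld until the infection has resolved or stabilized. Then "treatment with selinexor may continue at the original dose". The section sets no upper grade and does not mention attribution. It names no restart dose for ibrutinib.
- **Section 6.2 (non-hematologic toxicity).** It has no infection table, so its general text applies. At Grade 3: "For all other grade 3 non-hematologic toxicities possibly related to study therapy, hold the causative agent" (both drugs if the cause is unclear), and on recovery "resume treatment with a decrease in the dose of ibrutinib by 140 mg or selinexor by one dose level". The Grade 4 rule covers toxicities "that are at least possibly attributed to selinexor or ibrutinib should result in permanent discontinuation of the causative agent", and both drugs stop if neither can be singled out. Its only qualifier is a duration condition for transaminases and electrolytes.
- **Section 5.18 (selinexor supportive care table).** The last row, for other selinexor-related events, asks at Grade 3 or 4 for interruption and then a reduction of one dose level.
- **Section 6 (opening).** "Toxicities that occur in cycle 1 that are DLTs (Section 4.2) will result in protocol removal". The modifications set out below it are for adverse events "that are not defined as DLTs and / or occur in cycles 2 and higher will lead to dose delays and modifications".

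**The concern.** An infection is a non-hematologic event. If it is possibly related to study drug, Sections 6.4 and 6.2 both reach it, and Section 5.18 does too if it is selinexor-related. They point in different directions. At Grade 4 the gap is as wide as it can be: re-exposure at the original dose is permitted by one section and permanent discontinuation is called for by another.

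The first stake is patient safety, because two patients with the same serious event could be handled in opposite ways, each in line with a written rule. The second is interpretation. Section 13.8.1 provides for summaries of dose reductions and reasons for going off treatment as measures of tolerability (objective 1.2.1). In a multi-center trial, these would partly reflect which section was consulted. Cohort 3 is also sensitive: it has ten patients and judges the regimen on conversions after 14 cycles, so one patient stopped or continued is 1/10 = 10% of the cohort.

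**Working it through.** No arithmetic is involved. The check sets the rules side by side for an infection that is not handled as a Cycle 1 DLT, and then looks for any text that ranks them.

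**Step 1. Selinexor rule by section, where selinexor is a suspected cause**

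| Infection | Section 6.4 | Section 6.2 | Section 5.18 (if selinexor-related) |
|---|---|---|---|
| Grade 3 | Original dose permitted | Resume with a decrease | Reduce one level |
| Grade 4 | Original dose permitted | Permanent discontinuation | Reduce one level |

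At Grade 4 the three columns give three outcomes. At Grade 3 they give two.

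**Step 2. How attribution changes this**

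- Clearly unrelated infection: neither the Section 6.2 rules nor the Section 5.18 row applies. Section 6.4 stands alone and nothing conflicts.
- Selinexor suspected, or cause not separable: the Section 6.2 conflict on selinexor arises as tabulated.
- Ibrutinib alone suspected: Section 6.2 acts on ibrutinib (decrease at Grade 3, stop at Grade 4). Section 6.4 holds ibrutinib only until the infection resolves or stabilizes and is silent on its dose afterwards. At Grade 4 this leaves open whether ibrutinib restarts at all; at Grade 3 it leaves open the dose.

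**Step 3. Text that might rank the rules**

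- The tie-break in Sections 6 and 6.2, which selects the adjustment giving the lowest dose, is worded for a patient with several adverse events. Here there is one event under several rules.
- Section 6.5 lists the exceptions to the preceding guidelines: alopecia and reversible electrolyte abnormalities. Infection is not among them.
- Section 6.7 requires the principal investigator to be consulted on every delay, modification and reintroduction. It names who is consulted, not which rule prevails.
- Section 8.1.5 sends the reader to the infection section for dose adjustment, under an outdated section number. This favours Section 6.4 but does not say that it displaces Section 6.2 or 5.18.

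**Step 4. Two tenable readings**

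One reader may take Section 6.4 as the complete infection rule, whatever the attribution. Another may confine it to unrelated infections and use Sections 6.2 and 5.18 for the rest. Nothing in the text excludes either reading, and even the second leaves Sections 6.2 and 5.18 in disagreement at Grade 4.

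**The case against.** The best defence is that a specific rule beats a general one. Section 6.4 is devoted to infection, Section 8.1.5 points to it, and the Grade 3 sentence in Section 6.2 is residual, covering only toxicities without their own guideline. The hypertension table in Section 6.2 also departs from the general Grade 4 rule: it lets ibrutinib return at the same dose after a first related Grade 4 event. This carries real weight at Grade 3. It carries less at Grade 4, where the rule is not residual and has no infection carve-out, and it does not answer the reduction in Section 5.18.

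Section 6.4 is also permissive. A site that reduces or stops does not breach it, so these are not two opposed mandates. That stands, but permission to resume the original dose is still incompatible with a rule calling for permanent discontinuation.

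Section 6.7 means that restart is not left to a site alone. That also stands and should reduce variation in practice. It does not tell the principal investigator which section to apply.

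Two stronger readings are tempting but unsupported:

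- *Cycle 1 removal is unresolved.* The opening of Section 6 sends Cycle 1 DLTs to removal before the later subsections apply. Its linking words are loose, but the order is stated.
- *The DLT count depends on which section a site follows.* Section 5.3 defines a DLT by event, grade, duration and attribution, not by later dosing. A Cycle 1 infection meeting that definition counts whether or not drug is restarted, and Section 5.3 requires any exception to be reviewed and documented.

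**Conclusion.** The point holds as a contradiction between dose rules, limited to infections at least possibly related to study drug and not handled as Cycle 1 DLTs. It is firm at Grade 4, with up to three incompatible selinexor outcomes. It is weaker at Grade 3, with two outcomes and a reasonable argument that Section 6.4 governs. A separate gap is the missing ibrutinib restart dose in Section 6.4.

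The conclusion assumes that infection counts as a non-hematologic toxicity, which follows from its absence from the hematologic tables in Section 6.1. Frequency cannot be stated, because the documents give no infection rate by grade for the combination. The primary endpoint and the dose-finding rule are untouched. The point should be fixed because the text allows opposite handling of the same serious event, but it does not threaten the design.

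**What to change.** Reconcile Sections 5.18, 6.2 and 6.4. State, by grade and by attribution, which section governs an infection, and cross-refer from the other two. State whether Section 6.4 or Section 6.2 governs the ibrutinib restart dose. Correct the outdated section number in Section 8.1.5 at the same time. Which dose rule applies is a clinical decision for the sponsor and the investigators; none is proposed here.

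The cost is amendment wording and site notification. No change to data collection or sample size is needed.
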